**LIST OF ABBREVIATIONS**

AE	Adverse Event/Adverse Experience
ED	Erectile Dysfunction
HIPAA	Health Insurance Portability and Accountability Act
IPP	Inflatable penile prosthesis
PHI	Protected health information
PP	Penile Prosthesis
PTT	Penile traction therapy

## Study Summary

Title	Penile Lengthening Pre-Penile Prosthesis Implantation
IRB Protocol Number	17-011052
Methodology	Open enrollment
Overall Study Duration	3 years
Subject Participation Duration	3 months
Objectives	Compare length of penile prosthesis inserted after traction therapy
Number of Subjects	80
Diagnosis and Main Inclusion Criteria	Men undergoing placement of a penile prosthesis
Study Device	RestoreX®, penile traction therapy
Duration of Exposure	Subjects will use device for 30 minutes, 3 times a day
Reference therapy	Use of the device will be compared against a control group using no traction therapy
Statistical Methodology	Statistical comparisons will be made comparing total length of prosthesis inserted between those using and not using traction, stratified by baseline penile length.

## 1 Introduction

This document is a protocol for a human research device study. This study will be carried out in accordance with the procedures described in this protocol, applicable United States government regulations and Mayo Clinic policies and procedures.

### 1.1 Background

Men with erectile dysfunction (ED) refractory to conservative therapies are often recommended to undergo placement of an inflatable penile prosthesis (IPP). However, one of the most common complaints after surgery is that the men feel that their penis is shorter than what it was previously. This is likely due to one of several factors including the underlying disease process which resulted in loss of penile length, effects of aging on penile length (loss of elasticity; increased fibrosis), changes in abdominal physiology (development of pre-pubic fat pad that obscures the penis), and recall bias (incorrect assumptions on prior penile length).

Several attempts have been made by investigators to optimize penile length prior to placement of the penile prosthesis, including adjunctive surgical maneuvers (excision of suprapubic fat pad, release of suspensory ligament, direct penile extension), use of injectable materials, and pre-operative use of penile traction therapy (PTT). In a small pilot study of 10 men undergoing IPP, Levine and colleagues recommended the use of the Andropenis PTT  $\geq 2$  hours daily for 2-4 months. At 15 months follow-up, patients achieved a +1.6 cm increase compared to pre-traction stretched length, and +0.9 cm increase following penile prosthesis (PP). Results from a non-validated satisfaction questionnaire demonstrated that no patients reported loss of length following surgery. Unfortunately, the study did not include a control group, thus limiting the conclusions which may be drawn.

Compared to other options, PTT offers several potential advantages in that it is minimally-invasive, does not increase the morbidity of surgery, and has not been shown to result in any long-term side effects.

Recently, Mayo Clinic licensed a new PTT concept to PathRight Medical, who subsequently developed the RestroreX PTT device. This is classified as a Class I device, not requiring clinical human trials. The purported benefits with the RestroreX device over other PTT systems include ability to generate constant traction, user-feedback on appropriate use, improved comfort, and ability to track improvements. The device is currently utilized in 30-minute intervals, with up to 3 sessions performed per day.

Given the clinical issue of dissatisfaction with penile length post IPP, the potential role for PTT, and limited amount of data available, we sought to perform a clinical trial evaluating the effect of PTT on increasing the total length of prosthesis which can be inserted. We additionally sought to determine if PTT resulted in improved post-operative satisfaction on total penile length achieved.

## 1.2 Investigational Device

RestoreX is a PTT device developed by PathRight Medical using technology licensed from the Mayo Clinic. The device is classified as class I (orthotic) and does not require clinical trials to prove safety or efficacy. Mayo Clinic is currently conducting a randomized clinical trial to evaluate several clinically relevant factors including safety, comfort, and preference and to provide preliminary data on dosing and efficacy (IRB 17-001283).

The device has two functional aspects. The first is the ability to provide direct traction on the penis. The second is the ability to provide counter-bending forces, to treat conditions such as Peyronie's disease (bent penis). In the current study, only the direct traction aspects of the device will be investigated.

Men will enter into either the control arm (no treatment) or the treatment arm and will be recommended to utilize the device for 30 minutes, 3 times daily for 3 months prior to placement of an IPP.

## 1.3 Preliminary Data

Currently, there is a small amount of preliminary data available on the RestoreX® instrument. During the developmental phase of the device, a quality improvement project was performed to evaluate the clamping portion. It was determined that the clamp represented the most critical aspect of the device, as this was where the majority of discomfort occurred with other devices. Additionally, the clamp needed to provide sufficient friction to allow adequate traction without having the glans of the penis dislodge from the device.

A total of 15 patients participated in the quality improvement project and had the clamps applied under direct supervision for 30 minutes. After the 30 minutes, all patients reported 0/10 pain, and only minimal transient erythema was documented by the physician. The clamp was again applied, and traction forces were administered to determine if the clamp was able to remain intact despite stretching forces applied. This also resulted in a successful outcome, with all patients able to successfully achieve a minimum required tension of 1 kg, with a 36% safety factor achieved before any discomfort was reported among any patient. During the testing, patients reported improved comfort with the use of a wrap such as gauze or Coban, which permitted additional traction in all patients.

Very limited data are available on the efficacy of PTT in men undergoing placement of an IPP. As previously noted in the introduction, a small pilot study of 10 men undergoing IPP demonstrated a +1.6 cm increase in penile length compared to pre-traction stretched length and 0% of men reporting loss of length following surgery. The study has several notable limitations including a lack of control group and use of more relevant clinical measure such as length of device inserted.

Regarding background data on the RestoreX device, currently, Mayo Clinic is conducting a randomized clinical trial evaluating its role in men with PD (IRB 17-001283). Initial data are expected by the end of 2018.

## **1.4 Study Rationale and Risk Analysis (Risks to Benefits Ratio)**

### **1.4.1 Study Rationale**

PTT has been shown to improve penile length in several clinical scenarios, including following penile surgery, as a primary lengthening therapy, and in men with conditions which shorten the penis such as Peyronie's disease. Very preliminary data suggest a possible role for PTT prior to placement of an IPP to optimize outcomes and address a common complaint of reduced penile length. The current study is designed to address this gap in the literature.

### **1.4.2 Potential Benefits**

There are several potential benefits to using PTT prior to IPP placement. The most notable is the ability to place a larger device. As reduced penile length is a very common complaint post-operatively, any therapy which addresses this issue offers the potential benefit of enhancing overall patient satisfaction. Perhaps more importantly though, currently there are several adjunctive surgical techniques which are used to increase penile length. These often are very morbid procedures and may result in significant consequences including necrosis of the glans penis, need for additional surgeries, infections, and early device failures, among others. Given the minimally-invasive nature of PTT, any data demonstrating efficacy of this therapy offers potential benefits over the more invasive alternatives.

## **1.5 Anticipated Duration of the Clinical Investigation**

The overall study will be scheduled for 3 years, to permit adequate time for enrollment and follow-up. The intervention phase will include 3 months of treatment (for the treatment arm) and up to 1 year follow-up.

# **2 Study Objectives**

## **2.1 Primary Objective**

1. The primary objective is to assess the length of the penile prosthesis inserted into subjects following completion of RestoreX® traction therapy compared to control groups (no treatment).

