### **3.5 Study Schema**

During the initial scheduled clinic appointment, the patient will receive a description of the study, and informed consent. Potential subjects will be notified about the two groups for the study: Treatment (PTT for 30 min 3x/day for 3 months) or No Treatment (control). Subjects planning to have their IPP procedure immediately and do not want to utilize traction therapy will be considered for the control group. Subjects who wish to wait for placement of IPP and are interested in utilizing traction will enter into the treatment group. Those consenting will receive initial study assessments and subjects who take part in the treatment group will be educated on how to use the device properly.

Patients will then be given a baseline questionnaire to complete and, if assigned to the treatment group, begin using the device. Patients in the treatment arm will record a daily journal of their usage of the device.

After 3 months (+1.5 months permitted), patients in the treatment arm will return for their scheduled procedure (control arm patients will undergo surgery without a 3-month delay). Only those who utilized the device for 3 months will be asked to complete a follow-up questionnaire at this time. Patients will also be encouraged to self-report any additional adverse events (AE's) that they encountered over the 3 months of using the therapy.

During surgery, data will be recorded by the surgeon to indicate type, length and approach taken for penile prosthesis implanted as well as any complications of penile prosthesis implantation. These complications may include urethral perforation, corporal perforation, device malfunction, bowel injury or vascular injury; all of which are standard potential complications of the surgery.

Following surgery, patients will be seen in the clinic based on the standard routine clinical practice. During these follow-up appointments, penile length measurements will be performed and recorded.

Patients will also be sent questionnaires by email or by mail (if email not available) at 3, 6, and 12 months post-operatively. If a patient has not returned their questionnaire within 2 weeks, a follow up phone call to the patient will be placed as a reminder. Alternatively, patients may answer the questions over the phone if that method is preferable.

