### 5.2 Statistical Analysis

Analyses will be performed using comparisons within patients of same baseline penile stretch length and between groupings of varying lengths. Comparison of device length implanted will be made for subjects using the traction device compared to those who did not utilize traction. Comparisons will also be made on other subjective and objective variables obtained including number of adverse events, complications, subjective responses to questionnaires, or other information. Pre- and post-operative penile lengths will also be compared within individuals. All data will be normalized based on pre-operative stretched penile length.

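### Does the plan need to name a primary analysis set because sections 2.1, 3.5 and 5.2 describe the traction group in different words?

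*Combined protocol and SAP*

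**What the plan says.** Three places bear on who is compared.

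- **Section 2.1 (Primary Objective)**: the outcome is the "length of the penile prosthesis inserted into subjects following completion of RestoreX® traction therapy compared to control groups (no treatment".
- **Study Summary (Statistical Methodology)** and **section 5.2**: the Summary speaks of "comparing total length of prosthesis inserted between those using and not using traction, stratified by baseline penile length", and 5.2 says "Comparison of device length implanted will be made for subjects using the traction device compared to those who did not utilize traction".
- **Section 3.5 (Study Schema)**: group entry follows the patient's wish. "Subjects who wish to wait for placement of IPP and are interested in utilizing traction will enter into the treatment group"; men who want surgery at once and no traction are considered for control.

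Other lines show how the words are used. The Summary's Reference therapy line reads "Use of the device will be compared against a control group using no traction therapy", and section 1.2 says "Men will enter into either the control arm (no treatment) or the treatment arm". On timing, section 3.5 has "After 3 months (+1.5 months permitted), patients in the treatment arm will return for their scheduled procedure". On records, it has "Patients in the treatment arm will record a daily journal of their usage of the device".

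The plan contains no intention-to-treat, per-protocol or as-treated definition, and no threshold for use or completion.

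**The concern.** Taken literally, completing traction, using it and entering the traction arm are three different groupings, and the first two depend on what a man did after enrolment. Controls have nothing to complete, so a completers-only rule would select one arm on persistence and leave the other untouched. If persistent men would have received longer or shorter implants anyway, the contrast is shifted for reasons unrelated to traction.

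Early stopping is foreseeable. The regimen is three sessions a day for 3 months, compliance is a secondary objective (2.2), and section 6.6.2 provides for discontinuing the device. With no set written down, the grouping could also be settled after the results are known.

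**Working it through.** **1. Who is classified differently?** The wordings side by side, for men who are implanted:

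| Man | 2.1, read literally | Summary and 5.2 | Arm entered (3.5) |
|---|---|---|---|
| Control | control | not using | control |
| Treatment arm, completes traction | treated | using | treatment |
| Treatment arm, stops early | outside treated group | using | treatment |
| Treatment arm, never starts | outside treated group | not using | treatment |

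Controls and completers fall in the same place throughout. The two statistical passages agree with each other, and they differ from arm entered only for never-starters. Section 3.5 describes enrolment and is not an analysis statement. The one wording that could remove early stoppers is 2.1, and only if completion is an eligibility condition and not a time point.

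**2. The plan's only attrition figure.** Section 3.4 accrues 40 per arm to have at least 20 per arm complete the study. The implied loss is 1 − 20/40 = 50%, and 20/(1 − 0.5) = 40 per arm, 80 in total, which agrees. This covers all losses over the whole study in both arms. It is not a rate of stopping traction, and it does not say that only completers are analysed.

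**3. Bias if 2.1 were a completers-only rule (illustration).** The documents give no SD, effect, alpha or stopping rate. Assumed: two-sided 5%, SD 1, 40 enrolled per arm, everyone implanted, no baseline adjustment, no traction effect, arms otherwise alike. Let f be the stopping fraction and g the completer-minus-stopper gap. The arm mean equals the control mean, so (1 − f)·completer mean + f·stopper mean = control mean, and the completer mean exceeds the control mean by f × g.

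| f | Completers vs controls | Bias, g = 0.5 SD | Bias, g = 0.25 SD | False-positive rate, g = 0.5 SD |
|---|---|---|---|---|
| 10% | 36 vs 40 | 0.05 | 0.025 | 5.5% |
| 25% | 30 vs 40 | 0.125 | 0.0625 | 8.0% |
| 50% | 20 vs 40 | 0.25 | 0.125 | 14.6% |

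The rates come from the noncentral t distribution with noncentrality f·g / √(1/n₁ + 1/40). At f = 50%, that is 0.25/√(1/20 + 1/40) = 0.25/0.274 = 0.91. The sign of g is unknown, so the bias may run either way.

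**4. What grouping by arm entered would cost.** Assumed: completer effect 0.5 SD, no gain in stoppers, no selection gap. The by-arm effect is 0.5 × (1 − f).

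| f | By-arm effect | Power by arm (40 vs 40) | Power, completers |
|---|---|---|---|
| 10% | 0.45 | 51.1% | 57.5% |
| 25% | 0.375 | 38.1% | 53.2% |
| 50% | 0.25 | 19.7% | 43.5% |

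For 80% power the completer effect would have to be 0.70/0.85/1.27 SD by arm, against 0.65/0.69/0.78 SD among completers.

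**5. Is anything lost by leaving the plan as it is?** Prosthesis length is recorded in both arms (Tables 1 and 2), and the diary records use in the traction arm. Arm entered, any use and completion can all be tabulated from data already planned.

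**The case for a change.** The strongest case for a change is pre-specification. The study is open and unrandomised, an investigator invented the device (8.2, reviewed and cleared by the institution), and people associated with the manufacturer may help with the analysis (5.1). One sentence naming the set would cost almost nothing. Grouping by arm entered would avoid adding a second, one-sided selection to the confounding already present.

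Part of this stands. No passage classifies implanted early stoppers or never-starters, and a literal completers-only primary analysis could mislead. Any report should say which grouping was used and how many men the choice affects.

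The rest is weaker. The selection argument does not reach the using/not-using wording of the section that governs the analysis, because an early stopper remains a user there. The illustrated bias leaves out the plan's stratification and normalisation by baseline length, which may remove part of it. The preferred remedy is also contestable. In a randomised trial, analysis by arm preserves the randomisation; here the men choose their arm, so there is none to preserve. Section 1.1 asks about the effect of traction on the length that can be inserted, and a defined-use comparison also answers that question.

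**Conclusion.** No change to the plan follows. The sections leave a detail unstated, but they contain no rule shown to give a wrong result. The two statistical passages agree, completion in 2.1 fits the 3-month timing of surgery in 3.5, and the Reference therapy line and section 1.2 support reading use and no treatment as names for the two arms. A competent analyst would compare the groups as entered or as using traction, account for the few men who fall between, and show the alternative.

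The harm arises only under the literal completers-only reading. There it runs from negligible (5.5% false positives against a nominal 5%, at 10% stopping) to material (about 15%, at 50% stopping with a 0.5 SD gap and every stopper implanted). All of those inputs are assumed. Making arm entered the primary grouping would, under the power assumptions above, cost about 6 percentage points of power at 10% stopping (57.5 − 51.1 = 6.4) and about 24 at 50% (43.5 − 19.7 = 23.8), more than half of the completer power at that rate. It would leave the confounding from self-selected arms untouched. That is a judgement for the study team, and the documents do not dictate the answer. This conclusion would change if a later analysis document made completers-only the primary comparison.

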## 2.2 Secondary Objective

1. Compare patient compliance with traction device.
2. Compare patient reported satisfaction with use of traction device.
3. Evaluate any adverse events (AEs) with use of RestoreX® for penile lengthening.
4. Compare intra- and/or post-operative complication rates.
5. Compare pre- and post-operative stretched penile lengths.
6. Compare patient satisfaction scores including satisfaction with overall penile length.

## 3 Study Design

### 3.1 Subject Selection

#### 3.1.1 Inclusion Criteria

- Men undergoing placement of a penile prosthesis
- >18 years old
- Must be the first time a penile prosthesis is implanted
- Undergoing implantation of a 3-piece inflatable penile prosthesis

#### 3.1.2 Exclusion Criteria

- Prior ischemic priapism
- Any prior penile prosthesis surgeries
- Any prior penile surgeries other than circumcision
- Undergoing malleable penile prosthesis or Ambicor device

### 3.2 Setting

The current study will be conducted at both the Mayo Clinic in Rochester, MN (Department of Urology) and Washington University in Saint Louis, Division of Urologic Surgery. All patients will be recruited from Drs. [name]'s (Mayo Clinic) and [name]'s (Washington University) clinical practices.

### 3.3 Recruitment

Drs. [name] and [name] will identify potential participants for recruitment in the study from their own practice and based on the inclusion and exclusion criteria. Patients will be notified of the study at the time of their planned clinic visit and those who would be interested in proceeding with the trial will be invited to meet with a study coordinator, at which time details of the study itself will be reviewed. No financial incentives will be provided to participate in the trial; however, participants would be given a RestoreX® device at no

charge if assigned to the treatment group. Patients will not be charged for any visits related to the study, and no labs or other testing will be obtained which require payment.

### **3.4 Consent and Accrual**

During the patient's consultation appointment, they will receive a description of the study and if the patient expresses interest in participating, a formal consent will be reviewed (see **Attachment – Consent Form**).

If the patient successfully completes the consenting process, they will undergo initial study penile length assessments (described later in the protocol). Those wishing additional time to consider participation may be rescheduled to a later date if desired.

At the time of consent, all participants will be assigned a study identifier, with a master list maintained in a password protected database (Mayo server) linking the patient to the identifier. A total of 40 patients will be accrued into each arm of the study, for a total of 80 patients accrued overall. It is estimated that 80 patients will need to be accrued in order to achieve a minimum of 20 subjects in each arm that will complete the study from start to finish.

No limitations will be applied to either clinical site for enrollments, such that it is possible that one clinical site may enroll 100% of the patients.

### **3.5 Study Schema**

During the initial scheduled clinic appointment, the patient will receive a description of the study, and informed consent. Potential subjects will be notified about the two groups for the study: Treatment (PTT for 30 min 3x/day for 3 months) or No Treatment (control). Subjects planning to have their IPP procedure immediately and do not want to utilize traction therapy will be considered for the control group. Subjects who wish to wait for placement of IPP and are interested in utilizing traction will enter into the treatment group. Those consenting will receive initial study assessments and subjects who take part in the treatment group will be educated on how to use the device properly.

Patients will then be given a baseline questionnaire to complete and, if assigned to the treatment group, begin using the device. Patients in the treatment arm will record a daily journal of their usage of the device.

After 3 months (+1.5 months permitted), patients in the treatment arm will return for their scheduled procedure (control arm patients will undergo surgery without a 3-month delay). Only those who utilized the device for 3 months will be asked to complete a follow-up questionnaire at this time. Patients will also be encouraged to self-report any additional adverse events (AE's) that they encountered over the 3 months of using the therapy.

During surgery, data will be recorded by the surgeon to indicate type, length and approach taken for penile prosthesis implanted as well as any complications of penile prosthesis implantation. These complications may include urethral perforation, corporal perforation, device malfunction, bowel injury or vascular injury; all of which are standard potential complications of the surgery.

Following surgery, patients will be seen in the clinic based on the standard routine clinical practice. During these follow-up appointments, penile length measurements will be performed and recorded.

Patients will also be sent questionnaires by email or by mail (if email not available) at 3, 6, and 12 months post-operatively. If a patient has not returned their questionnaire within 2 weeks, a follow up phone call to the patient will be placed as a reminder. Alternatively, patients may answer the questions over the phone if that method is preferable.

The subject's clinical records will also be reviewed up to 12 months post-operation to check for any complications relating to the surgery including a need for revision surgery, infection or hospitalizations.

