### 8.2 Conflict of Interest

[name] is the inventor and developer of the RestoreX® device. His conflict has previously been reviewed with the Mayo Clinic Conflict of Interest Review Board, and following review, it has been determined that [name] is able to conduct these studies as a Primary Investigator.

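### Arm follows patient preference and can be foreseen before enrolment; with no common entry rule, consecutive invitation or screening log, selective entry of controls cannot be excluded or assessed

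*Combined protocol and SAP*

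**What the plan says.** **Allocation (3.5 Study Schema).** There is no randomisation. For men planning immediate surgery the text says that those who "do not want to utilize traction therapy will be considered for the control group". For the others: "Subjects who wish to wait for placement of IPP and are interested in utilizing traction will enter into the treatment group". The preference is expressed once the study is described: "Potential subjects will be notified about the two groups for the study".

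**Recruitment (3.3).** The surgeons "will identify potential participants for recruitment in the study from their own practice and based on the inclusion and exclusion criteria". Men who show interest "will be invited to meet with a study coordinator, at which time details of the study itself will be reviewed".

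**Accrual and baseline (3.4).** Forty men are accrued per arm, 80 in all, to secure at least 20 completers per arm. Study length is measured after consent: "If the patient successfully completes the consenting process, they will undergo initial study penile length assessments". The master list described there covers consented participants only.

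**Analysis (Study Summary; 5.2).** Implant length is compared with stratification by baseline length, and all data are to be normalised to pre-operative stretched length.

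**Interest (8.2).** One investigator "is the inventor and developer of the RestoreX® device". The same section says that the institution's conflict-of-interest board reviewed this and allowed him to act as a Primary Investigator.

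**The concern.** In a preference-based comparison the result depends on who enters each group as well as on what each man chooses. A man's arm turns largely on whether he wants surgery now or later, and his treating surgeon may already know that when deciding whether to mention the study. The plan gives control entry a conditional wording, with no criterion for what the condition is, and nothing obliges the surgeons to approach every eligible man.

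If the immediate-surgery men who enter tend to be those expected to take a shorter implant for their baseline length, traction appears to work when it does not. If they tend to be the opposite, a real effect is hidden. The impression behind such a choice (expected tissue quality, for example) need not be recorded anywhere, so adjustment cannot recover it. Without a log of eligible men not enrolled, the report cannot show that the controls represent the immediate-surgery men in these two practices.

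**Working it through.** **1. The plan's own figure.** Twenty completers out of 40 accrued implies 50% attrition: 20 / (1 − 0.5) = 40 per arm, and 2 × 40 = 80. The accrual arithmetic reproduces. The plan gives no alpha, power, effect size or SD, so the 20 itself cannot be derived.

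**2. What the text fixes and what it leaves open.**

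| Question | Control | Treatment |
|---|---|---|
| What decides the arm | Man's preference | Man's preference |
| Entry wording (3.5) | Conditional, no criterion | Unconditional |
| Eligibility criteria apply (3.3) | Yes | Yes |
| Consent needed (3.4, 3.5) | Yes | Yes |
| Every eligible man to be invited | Not stated | Not stated |
| Eligible men not enrolled to be logged | Not stated | Not stated |

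The gap does not depend on the verb. Even if the two entry wordings matched, nothing says which eligible immediate-surgery men fill the 40 places.

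**3. Illustrative size.** From the documents: 40 per arm at accrual, 20 per arm as the minimum of completers. Assumed: M eligible controls, of whom 40 enter; correlation r between the recruiter's choice and implant length given baseline length; no traction effect; two-sided 5% t test.

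Entered fraction p = 40/M. Selection intensity i = φ(z_p)/p, where φ is the standard normal density and z_p the p-quantile. Shift of the control mean = r × i, in SDs of implant length given baseline length. Noncentrality = shift × √(n/2), and the error is the noncentral-t probability beyond both critical values.

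Worked case, M = 80 and r = 0.3: p = 0.5, i = 0.399/0.5 = 0.798, shift = 0.3 × 0.798 = 0.239, noncentrality at n = 40 is 0.239 × √20 = 1.07, error 18.5%.

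| M | i | r | Shift (SD) | Error, 40 per arm | Error, 20 per arm |
|---|---|---|---|---|---|
| 50 | 0.350 | 0.2 | 0.07 | 6.1% | 5.5% |
| 50 | 0.350 | 0.3 | 0.11 | 7.5% | 6.2% |
| 60 | 0.545 | 0.2 | 0.11 | 7.7% | 6.3% |
| 60 | 0.545 | 0.3 | 0.16 | 11.2% | 8.0% |
| 80 | 0.798 | 0.2 | 0.16 | 10.9% | 7.8% |
| 80 | 0.798 | 0.3 | 0.24 | 18.5% | 11.4% |

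**4. Does the planned use of baseline length remove it?** A simulation (20 per arm, 4,000 runs, no traction effect) left out the top 20% of eligible controls on some factor and adjusted for baseline length by linear regression. The regression is an assumption, because 5.2 says only that data are normalised. The correlation of baseline with implant length was set at 0.5, 0.7 and 0.9.

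- Selection on baseline length: unadjusted bias 0.18 to 0.32 SD, adjusted bias about 0; false positives in favour of traction 2% to 3% (nominal 2.5%).
- Selection on a factor unrelated to baseline length: bias 0.15 to 0.31 SD after adjustment; false positives in favour of traction 21% to 22%.

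The second case is extreme, because the selecting factor accounts for all the variation that baseline length leaves. It shows that adjustment for length cannot reach such a factor; it does not estimate how strong the selection is.

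**The case against.** A reader might infer that the arm is known before a man is invited. The documents do not say so. In 3.3 identification rests on the eligibility criteria and details come later with the coordinator; in 3.5 the preference follows an account of both groups. What can be said is that the likely arm is foreseeable and can be known before consent.

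A reader might also infer that control entry is discretionary and treatment entry automatic. That rests on two verbs. Eligibility and consent apply to both groups, no section gives a surgeon power to refuse an eligible, consenting control, and the conditional wording may mean no more than being eligible subject to consent. Selective approach could also affect the treatment arm. These points stand, but they leave untouched the absence of any rule on invitation or entry and of any log.

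The inventor's role might suggest steering. Section 8.2 records an institutional review, names are removed so the text does not show whether the inventor is one of the two recruiters, and nothing indicates that selection occurred. The interest is a reason to want the safeguard and is not evidence of bias.

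Finally, the error rates use no document input except the group sizes. Pool size, correlation and direction are assumed, and with a pool of 50 and r = 0.2 the effect nearly vanishes. The planned handling of baseline length also deserves credit: done as a regression, it removes selection on length. Both objections limit the size of the concern. Neither removes the gap.

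**Conclusion.** The point holds in limited form. Arm follows an unconcealed preference that can be foreseen before enrolment, entry is worded differently for the two groups with no stated rule, and neither consecutive invitation nor a log is required. Selective entry, particularly of controls, therefore cannot be excluded or assessed from what the study will record. Stratifying by or normalising to baseline length limits selection on length only.

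Direction and size cannot be determined from the documents. The range of about 6% to 18% at 40 per arm (about 6% to 11% at 20 per arm) is conditional on pools of 50 to 80 and correlations of 0.2 to 0.3, and should be cited only as illustration. The matter is separate from, and less certain than, the men's own self-selection of arm, which exists whatever the entry wording means. The change is still worth making: it is cheap, it affects who enters the comparison, and men never recorded cannot be reliably reconstructed later.

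**What to change.** - **3.5:** use one entry rule for both groups. Every eligible, consenting man enters the group he chooses while that group is below its 40 places; state that a group closes to entry once full. The limit is needed because 3.4 fixes 40 per arm.
- **3.3:** require that every consecutive eligible man at each practice be invited while his group is open.
- **Log:** the existing study coordinator records each eligible man before study length is measured, with age, diagnosis, surgeon, preferred group, whether invited, whether enrolled, and the reason if not (including that the group was full).
- **Report:** give the counts of eligible, invited and enrolled men by preferred group and surgeon.

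The cost is a few sentences of protocol text, a little data entry, and slightly less freedom for the recruiters. The log reveals selection and does not fully prevent it, since a surgeon could still fail to mention the study. None of this corrects the men's own choice of arm, which would need a different design or separate analytic handling.
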